1. PROTOCOL SUMMARY

1.1. Synopsis

An open label, Phase 1, two-arm study to assess target occupancy and functional inhibition of JAK3 and TEC kinases by single doses of ritlecitinib in healthy adult participants

Brief Title:

A Phase 1 target occupancy study with ritlecitinib.

Rationale

This study aims to assess the target coverage/TO by ritlecitinib of two distinct families of kinases that are irreversibly bound (JAK3 and TEC kinases). In addition to TO, the study will include an assessment of the effect of ritlecitinib on pathways that functionally depend on either JAK3 or TEC kinases. Together these results will enable a more complete assessment of the relative degree of pathway coverage over a broad range of exposures and over a length of time that allows for recycling/production of new target (ie JAK3 and TEC family kinases).

Objectives and Endpoints

Objectives	Endpoints
Primary:	Primary:

 To characterize the TO of JAK3 and TEC kinases in peripheral blood mononuclear cells (PBMCs) after single oral dose of ritlecitinib 	
 Percent TO for JAK3 and TEC kinases (BTK, ITK, RLK, TEC and BMX)
Secondary:	Secondary:

 To evaluate the plasma exposure of ritlecitinib over 48 hours after single oral dose administration To evaluate the safety and tolerability of an oral dose of ritlecitinib when administered alone and in healthy adult participants 	
 Ritlecitinib plasma PK parameters 
 C_{max}, T_{max}, C_{last}, C_{av}, AUC_{last} and, AUC_{24} Assessment of TEAEs, clinical laboratory tests, and vital signs
Tertiary:	Tertiary:

 To characterize the relationship between TO in PBMCs and plasma ritlecitinib exposure over 48 hours after single oral dose 	
 Maximal inhibition (occupancy) by ritlecitinib (TO_{max}) Ritlecitinib plasma concentrations at 50% TO_{max} (IC_{50})

CCI

Overall Design

Brief Summary

This is a Phase 1, open label, parallel group, two-arm study to assess target occupancy and functional inhibition of JAK3 and TEC kinases by single doses of ritlecitinib in healthy adult participants.

Ritlecitinib is not expected to provide any clinical benefit to healthy participants. This study is designed to evaluate JAK3 and TEC kinase inhibition data for further clinical development.

Number of Participants

Approximately 16 participants will be enrolled to study intervention.

Note: "Enrolled" means a participant's, or his or her legally authorized representative's, agreement to participate in a clinical study following completion of the informed consent process and screening. A participant will be considered enrolled if the informed consent is not withdrawn prior to participating in any study activity after screening. Potential participants who are screened for the purpose of determining eligibility for the study, but do not participate in the study, are not considered enrolled, unless otherwise specified by the protocol.

Intervention Groups and Duration

Single doses of 50 mg and 200 mg are being used in the study which are expected to encompass concentrations observed in patient populations at clinically relevant doses.

Participants will be enrolled to receive either 50 mg or 200 mg single dose of ritlecitinib on Day 1. Blood samples to assess ritlecitinib PK, target occupancy and functional assays will be collected over 48 hours. Participants will remain in the CRU until Day 3 when they will be discharged after completion of study activities.

No dose changes/adjustments including flexible dosing; dose reductions, interruptions, or tapering is allowed as per study protocol.

Data Monitoring Committee or Other Independent Oversight Committee: No

[figure not shown]
Statistical Methods

Percent TO CCI

graphically and summarized by nominal timepoints using descriptive statistics. In addition, relationship between TO and plasma exposure of ritlecitinib will be assessed graphically and suitable exposure-response population models will be explored to quantify the relationship.

1.2. Schema

Figure 1. Study Schema

1.3. Schedule of Activities

The SoA table provides an overview of the protocol visits and procedures. Refer to the **STUDY ASSESSMENTS AND PROCEDURES** section of the protocol for detailed information on each procedure and assessment required for compliance with the protocol.

The investigator may schedule visits (unplanned visits) in addition to those listed in the SoA table, in order to conduct evaluations or assessments required to protect the well-being of the participant.

Table 1. Schedule of Activities for Study

Visit Identifier	Screening	D -1	D 1	D 2	D 3	ET	Follow-up ^l
Days Relative to Day 1 ^a	D -28 to D -2						
Informed consent	X						
CRU confinement		X	→	→	X		
Inclusion/exclusion criteria	X	X					
Medical/medication history	X	X					
Physical examination ^b	X	X					
Safety laboratory	X	X			X	X	
Demography (including height & weight)	X						
Contraception check	X	X			X	X	X
Pregnancy test (WOCBP only)	X	X			X	X	
Serum FSH (postmenopausal women only) ^c	X						
Urine drug testing	X	X					
Vital signs (supine BP and pulse rate)	X		X ^d		X	X	
12 Lead ECG (single)	X		X ^d		X	X	
HIV, HBsAg, HBcAb, HCVAb screen ^e	X						
QFT-G	X						
COVID-19 questionnaire ^f	X	X					
COVID-19 testing ^g	X	X					
COVID-19 check temperature ^h	X	→	→	→	X		
Retained Research Samples for Genetics (Prep D1) ⁱ			X				
Ritlecitinib dosing ^j			X				
Ritlecitinib PK blood sample ^k			X	X	X	X	
Functional assay blood sampling ^l			X	X	X		

PFIZER CONFIDENTIAL

Table 1. Schedule of Activities for Study

Visit Identifier	Screening					ET	Follow-up ^l
Days Relative to Day 1 ^a	D -28 to D -2	D -1	D 1	D 2	D 3		
Target occupancy blood sampling ^k			X	X	X		
CRU discharge					X		
Prior/Concomitant medication assessment	X	→	→	→	→	X	X
Serious and nonserious AE monitoring	X	→	→	→	→	X	X

- a. Day relative to start of study treatment (Day 1).
- b. Complete physical exam could be done at screening or admission on Day -1. Brief physical exam to be done only in case of finding at previous exam or new/open AE if applicable, at the discretion of the investigator.
- c. Any female who has been amenorrheic for at least 12 consecutive months.
- d. Collect before drug administration.
- e. All participants will undergo screening for Hepatitis B, Hepatitis C and HIV for eligibility. Please refer to [Section 5.2](#) for testing algorithm, reflex testing, and full eligibility criteria.
- f. Check exposure to positive participant, residence or travel in area of high incidence and COVID-19 related signs and symptoms.
- g. The testing for COVID-19 pathogen by PCR will be performed at each visit. For participants admitted for residence, a subsequent COVID-19 test will be performed after 4 days (ie, upon completion of 4 × 24 hours in-house), or if they develop COVID-19 like symptom(s).
- h. To be done twice daily during residence.
- i. Prep D1 Retained Research Samples for Genetics: If not collected on the designated collection day, collect at the next available time point when biospecimens are being collected in conjunction with a participant visit.
- j. Participants will be dosed with ritlecitinib following an overnight fast of at least 10 hours at approximately 08:00±2 hours.
- k. Refer to [Table 2](#) for details of ritlecitinib dosing, ritlecitinib PK sampling, functional assay blood sampling and target occupancy assay blood sampling.
- l. Participants will have a telephone contact at least 28 calendar days, and up to 35 calendar days after the last administration of the investigational product(s). At the discretion of the investigator, telephone contact may be substituted with an on-site visit in case of additional follow-up of open AEs or clinically significant laboratory findings.

Table 2. Table of Blood Sampling for Study Drug, Functional Assay and Target Occupancy

Study Day	1						2	3
Hours Before/After Dose	-1 ^a	0 ^a	1	2	4	8	24	48
Ritlecitinib dosing		X						
Ritlecitinib PK blood sampling		X	X	X	X	X	X	X
Target occupancy blood sampling	X	X	X	X	X	X	X	X

CCI

Target occupancy blood sampling

a. Predose samples.

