TO of JAK3 and the five TEC kinases by ritlecitinib has been demonstrated in vivo in NOD-scid IL2ry-null mice engrafted with human PBMCs which expresses JAK3 and TEC kinases.² Despite the large variation in occupancy measurements likely due to differing levels of human PBMC engraftment and the small number of mice (n=3) per time point, approximately 100% occupancy of JAK3 and most of the TEC kinases, except RLK, was observed in the spleen samples from early time points (0.25 to 5 h). A slower recovery of unbound BTK was seen compared to JAK3 and ITK due to relatively longer half-life of BTK (12-24 hours vs. 2-3 hours for JAK3/ITK). Since the PK profile of ritlecitinib is characterized by rapid absorption and rapid elimination half-life, it is important to study the relationship between TO of JAK3 and the TEC kinase family and the functional consequences of their inhibition over time by ritlecitinib in healthy participants to provide insights in assessing the impact in patients with inflammatory and autoimmune diseases. Based on the predicted PK for ritlecitinib, along with the need to assess target occupancy (and functional inhibition) in a predefined specimen collection window, at least 2 doses would be required to capture expected concentrations in patients at clinically relevant doses and also to better understand the expected hysteresis in exposure and response.

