The PK profile of ritlecitinib is characterized by rapid absorption median (T_{max} ranging from $\leq 0.75 - 1.5$ hour), rapid elimination ($t_{1/2}$ of ~ 2 hours) and are approximately dose proportional. Steady state generally appears to be reached by Day 4 for the QD regimens and Day 6 for the BID regimens based on similar median trough (predose) ritlecitinib beyond Day 6. Ritlecitinib has been evaluated at single oral doses ranging from 5 mg to 800 mg and multiple oral doses ranging from 50 mg to 400 mg QD and at 100 mg and 200 mg BID for 14 days. The clearance mechanisms for ritlecitinib in humans appear to be primarily by metabolism. Less than 10% of ritlecitinib is excreted unchanged in the urine.

In vitro and in vivo metabolite profiling suggested that the primary clearance mechanisms for ritlecitinib were both CYP450 mediated oxidation and glutathione related conjugation. Biliary excretion of ritlecitinib was limited in the rat and renal elimination was limited in humans. Reaction phenotyping in recombinant enzyme systems identified CYP3A4 as the predominant CYP450 isoform responsible for the metabolism of ritlecitinib, with minor contributions from CYP2C19 and CYP3A5.

CCI

Further information is available in the current version of the ritlecitinib IB.

Phase 2a Study in RA

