If an IV catheter is utilized for blood sample collections, ECGs and vital sign assessments (pulse rate and BP) should be collected prior to the insertion of the catheter.

For samples being collected and shipped, detailed collection, processing, storage, and shipment instructions and contact information will be provided to the investigator site prior to initiation of the study.

The total blood sampling volume for individual participants in this study is approximately 380 mL. The actual collection times of blood sampling may change. Additional blood samples may be taken for safety assessments at times specified by Pfizer, provided the total volume taken during the study does not exceed 550 mL during any period of 56 consecutive days.

To prepare for study participation, participants will be instructed on the information in the [Lifestyle Considerations](#) and [Concomitant Therapy](#) sections of the protocol.

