9.3.2. Secondary Endpoints

The secondary endpoints are pharmacokinetic parameters of ritlecitinib after single oral dose.

[figure not shown]
PK parameters will be derived, given available data, following single dose administration from the concentration-time profiles for ritlecitinib as follows:

Parameter	Definition	Method of Determination
AUC ₂₄	Area under the plasma concentration-time curve from time 0 to 24 hours	Linear/Log trapezoidal method
AUC _{last}	Area under the plasma concentration-time curve from time 0 to the time of the last quantifiable concentration (C _{last})	Linear/Log trapezoidal method
C _{av}	Average plasma concentration from time 0 to the time of the last quantifiable concentration	AUC ₂₄ /24
C _{max}	Maximum plasma observed concentration	Observed directly from data
C _{last}	Plasma concentration at 48 hours post-dose	Observed directly from data
T _{max}	Time to reach C _{max}	Observed directly from data as time of first occurrence

Concentrations will be assessed graphically. Concentrations (by nominal timepoints) and PK parameters will be summarized using descriptive statistics.

[figure not shown]

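### The first post-dose PK sample is at 1 h although the protocol reports median Tmax from 0.75 h or less to 1.5 h, so observed Cmax and Tmax may miss early peaks and AUC24 is likely understated; one 2 mL sample at 0.5 h would largely cure this

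*Protocol*

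**What the plan says.** The time row of Table 2 reads "Hours Before/After Dose -1 ^a 0 ^a 1 2 4 8 24 48", where the first two columns are predose. The row "Ritlecitinib PK blood sampling" is marked at 0, 1, 2, 4, 8, 24 and 48 h. Target occupancy (TO) is marked at the same times and also at -1 h. Neither has a draw between dosing and 1 h.

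Protocol section 2.2.4 describes the earlier experience as "rapid absorption median (T_{max} ranging from $\leq 0.75 - 1.5$ hour), rapid elimination ($t_{1/2}$ of ~ 2 hours".

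Protocol section 9.3.2 and SAP Table 2 define Cmax as "Maximum plasma observed concentration" and determine Tmax as "Observed directly from data as time of first occurrence". AUC24 and AUClast use the linear/log trapezoidal rule, and Cav is AUC24 divided by 24. SAP 6.2.1 specifies non-compartmental methods, and SAP 5.3 uses actual sampling times. Protocol 8.4.1 tolerates a 10% deviation up to 10 h after dosing, which is 6 minutes at the 1 h sample. The same section allows times to change but fixes the number of samples.

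**The concern.** The schedule and the reported Tmax range come from the same protocol and do not fit well together. If a participant peaks before the first sample, the highest observed value lies on the falling limb. Cmax is then too low and Tmax is recorded as 1 h.

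The area is affected as well. A straight line from zero to the 1 h value cuts under a curve that rises steeply and then bends, so AUC is understated even when the peak falls at 1 h. In all, five of the six secondary PK parameters (all but Clast) can be distorted. Values missed in the first hour cannot be recovered by later non-compartmental analysis. The plasma exposures are also the input to the exposure-occupancy relation that the study is meant to describe.

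**Working it through.** The plan gives no figure for the adequacy of its sampling times, so there is none to reproduce. The losses below are illustrative.

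**Inputs from the documents.** Sampling times (Table 2); median Tmax from 0.75 h or less to 1.5 h and half-life about 2 h (section 2.2.4); derivation rules (section 9.3.2).

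**Assumptions.** One-compartment oral model, scaled to unit dose and volume: C(t) = ka/(ka - ke) × [exp(-ke·t) - exp(-ka·t)]. Here ke = ln 2 / half-life, and ka is solved from Tmax = ln(ka/ke)/(ka - ke). Half-life is varied from 1 to 2 h. The shorter values are included because Table 3 of the protocol gives Cmax/AUC48 of 247.44/(11.19 × 48) = 0.46 per h at 50 mg and 1085.10/(60.57 × 48) = 0.37 per h at 200 mg. At Tmax 0.75 h the model gives 0.27 per h with a 2 h half-life and 0.41 per h with a 1 h half-life. Tmax spread between participants is lognormal with CV 30-50%. The 24 h concentration is treated as quantifiable.

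**One case by hand (half-life 2 h, Tmax 0.75 h).**
- ke = 0.3466 and ka = 3.385. True Cmax = exp(-0.3466 × 0.75) = 0.771. The 1 h value is 0.750, so observed/true = 0.973, a loss of 2.7%.
- True area from 0 to 1 h = 0.624. The trapezoid gives 0.5 × 0.750 = 0.375. The shortfall of 0.249, over a total area of 1/ke = 2.885, is 8.6%. Later segments bring the AUC24 loss to 8.9%.
- With a 0.5 h value of 0.732, the two trapezoids give 0.183 + 0.370 = 0.553. The 0-1 h shortfall falls to 0.070/2.885 = 2.4%, and the total loss to 2.7%.

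**Typical profiles, percent below the true value.**

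| Tmax (h) | Half-life (h) | Cmax, planned | Cmax, with 0.5 h | AUC24, planned | AUC24, with 0.5 h |
|---|---|---|---|---|---|
| 0.5 | 2 | 11.1 | 0 | 12.1 | 4.0 |
| 0.5 | 1 | 18.1 | 0 | 21.0 | 6.6 |
| 0.75 | 2 | 2.7 | 2.7 | 8.9 | 2.7 |
| 0.75 | 1 | 3.9 | 3.9 | 13.9 | 4.5 |
| 1.0 | 2 | 0 | 0 | 6.6 | 2.3 |
| 1.0 | 1 | 0 | 0 | 9.9 | 4.2 |
| 1.5 | 2 | 3.9 | 3.9 | 4.5 | 2.5 |
| 1.5 | 1 | 4.5 | 4.5 | 6.4 | 4.2 |

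**Geometric mean Cmax with the assumed spread of Tmax.**
- Median Tmax 0.75 h: 4-9% low for half-lives of 1.2-2 h, and up to 9.6% low at 1 h. With a 0.5 h sample, 1-2% low.
- Median Tmax 0.5 h: 11-17% low for half-lives of 1.2-2 h, and 18-20% low at 1 h. With a 0.5 h sample, 1-4% low.
- Median Tmax 1.0 h: 2-5% low. With a 0.5 h sample, 1-2% low.

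**Tmax.** With a true median of 0.75 h, the share peaking before 1 h is Φ(ln(1/0.75)/σ). For CV 30% σ = 0.294, giving 84%; for CV 50% σ = 0.472, giving 73%. None of these participants can be recorded below nominal 1 h, or 0.9 h at the edge of the window.

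**Occupancy.** In an irreversible-binding turnover model (target half-life 2.5 h for JAK3/ITK and 18 h for BTK, within the ranges in protocol section 2.1; TOmax assumed at 50%, 80% and 95%), the highest TO on the planned grid is 96-100% of true TOmax in every scenario.

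**The case against.** The strongest reply is that the support is conditional. The low end of the Tmax range is not tied to a dose or formulation. The earlier studies described include a solution and a tablet, whereas this study gives capsules to fasted participants. If the capsule's median Tmax is 1 h or later, no systematic loss of Cmax from early peaks is expected. This stands for Cmax and Tmax. It does not remove the AUC24 shortfall, which persists at Tmax 1 h. It is also fair that nothing is tested, that a similar proportional loss at both doses would largely cancel in the dose-normalised plots, and that redactions near the PK summary and Table 2 may hide a rationale.

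A reader might go further and infer that the onset of occupancy is missed and the occupancy results are compromised. The documents do not support that.
- Onset and binding rate are not named endpoints. Percent TO is summarised by nominal time, and TOmax is barely affected.
- TOmax and IC50 are exploratory, estimated only if data permit, and kept out of the CSR (SAP 6.3.1).
- The mouse finding of about 100% occupancy "was observed in the spleen samples from early time points (0.25 to 5 h" comes from spleen, with three animals per time point, large variation and RLK excepted. If human occupancy were that fast, a 0.5 h sample would also sit on the plateau.
- With n = 8, an assumed residual SD of 10 points and the 50 mg Cmax, a 0.5 h TO sample cuts the standard error of the log binding rate by 73-82% when TO at 1 h is 96-99% and 0.5 h is still below the plateau. The cut is 1-10% when TO at 1 h is below 45%, and 1-12% when TO is already 84-94% at 0.25 h. Nothing in the documents places any human kinase in the favourable band.

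**Conclusion.** The point holds for the PK sampling, as a modest and inexpensive improvement. The gap before 1 h is certain. The direction of the AUC24 error is the same in every case examined, and it reaches about 9-14% at Tmax 0.75 h. Cav shares that percentage exactly, and AUClast contains the same first-hour segment. The Cmax and Tmax effects depend on whether the capsule's Tmax is early. All sizes depend on the assumed model form, half-life and spread; the documents fix only the sampling times, the Tmax range and the approximate half-life. The stronger statements, that Cmax is necessarily understated by a material amount or that the occupancy endpoints are lost, are not established.

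**What to change.** Add one 2 mL PK sample at 0.5 h post-dose to Table 2, and amend the statement in section 8.4.1 that the number of samples stays the same. The cost is a schedule amendment, one extra draw per participant during confinement, 16 more PK assays, and about 2 mL on the planned total: 380 + 2 = 382 mL. The stated condition is that the volume "does not exceed 550 mL during any period of 56 consecutive days".

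The added sample does not solve everything. If true Tmax is near 0.75 h, the typical recorded Tmax remains 1 h and the typical-profile Cmax loss of 3-4% stays. The gain there is in AUC and in participants who peak earlier.

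A paired 30 mL TO sample at 0.5 h is optional. It would take the total to 380 + 32 = 412 mL, plus any matching functional-assay volume, which is redacted and cannot be counted here. It is worth considering only if the sponsor expects occupancy to be near plateau at 1 h but still rising at 0.5 h.

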2. INTRODUCTION

Ritlecitinib (previously known as PF-06651600) is a potent, covalent, and irreversible inhibitor of JAK3 with high selectivity over the other three JAK isoforms (JAK1, JAK2, and TYK2). Ritlecitinib also inhibits irreversibly the TEC family kinases BTK, BMX, ITK, RLK, and TEC) with selectivity over the broader human kinase. Ritlecitinib is being developed for the treatment of UC, CD, AA, RA, and vitiligo.

2.1. Study Rationale

Inhibition of JAK3 by ritlecitinib is expected to modulate γ -common chain cytokine pathways, such as IL-7, IL-9, IL-15, and IL-21, but expected to spare inhibition of other JAK-dependent pathways that do not utilize JAK3, including IL-6 signaling and key immuno-suppressive cytokines, such as IL-10, IL-27 and IL-35.¹ Selective JAK3 targeting may reduce adverse effects from other JAK pathways, including cytopenia's (JAK2-dependent), cardiovascular events, malignancies, and severe infections. Inhibition of TEC kinases by ritlecitinib is expected to modulate T cell and B cell development and function (TEC kinases are activated downstream of the TCR and BCR). These effects by ritlecitinib on TCR signaling have been shown to inhibit the cytotoxic function of CD8+T cells and NK cells.² There is limited information on the degree of target occupancy by Ritlecitinib on JAK3 and TEC kinases (ie, irreversible kinase binding) in humans, and how TO and target turnover of both JAK3 and TEC kinases a) is regulated by drug half-life, and b) how TO translates into functional effects on specific cell types and pathways.³

TO of JAK3 and the five TEC kinases by ritlecitinib has been demonstrated in vivo in NOD-scid IL2ry-null mice engrafted with human PBMCs which expresses JAK3 and TEC kinases.² Despite the large variation in occupancy measurements likely due to differing levels of human PBMC engraftment and the small number of mice (n=3) per time point, approximately 100% occupancy of JAK3 and most of the TEC kinases, except RLK, was observed in the spleen samples from early time points (0.25 to 5 h). A slower recovery of unbound BTK was seen compared to JAK3 and ITK due to relatively longer half-life of BTK (12-24 hours vs. 2-3 hours for JAK3/ITK). Since the PK profile of ritlecitinib is characterized by rapid absorption and rapid elimination half-life, it is important to study the relationship between TO of JAK3 and the TEC kinase family and the functional consequences of their inhibition over time by ritlecitinib in healthy participants to provide insights in assessing the impact in patients with inflammatory and autoimmune diseases. Based on the predicted PK for ritlecitinib, along with the need to assess target occupancy (and functional inhibition) in a predefined specimen collection window, at least 2 doses would be required to capture expected concentrations in patients at clinically relevant doses and also to better understand the expected hysteresis in exposure and response.

